### ONLY A SMALL PROPORTION OF CANCER PATIENTS SUCCEEDED AT QUITTING SMOKING

The information from the Roswell Park study would suggest that approximately 30-40% of smokers attempt to quit at or around the time of their cancer diagnosis. A recent publication from a large, well-funded cessation service at Sloan-Kettering offering intensive cessation support, found that of over 4500 tobacco user referrals, 3430 (75%) were unreachable or refused cessation assistance. Of the over 1000 enrolled in the service, about 25% did not complete the protocol, 25% either died or were lost to follow-

up, and 43% reported no tobacco use at 6 months. In summary, the data from a large cessation service at a major cancer center suggest that these state-of-the art programs benefit only about 10% of smokers with cancer. This is, again, consistent with the findings above that suggest these individuals are heavily addicted and relatively refractory to cessation treatment, leaving about 90 percent who continue to expose themselves to smoke-derived carcinogens during the course of their therapy.

[figure not shown]
The Sloan-Kettering program assessed e-cigarette use among patients trying to quit smoking and found that as many as half of these patients were experimenting with e-cigarettes during 2013, but that e-cigarette use did not affect successful quit rates. This is becoming a common finding in population studies of e-cigarettes, in part because people receive mixed messages from the public health community regarding whether these products represent an appropriate substitute for smoking. In the present study, we will test the appeal and toxicity of e-cigarettes in smokers with cancer.

## **E-CIGARETTES**

### **WHAT ARE THEY AND HOW DO THEY WORK**

Electronic cigarettes, also known as e-cigarettes, create an inhalable nicotine aerosol by heating a liquid nicotine solution. Unregulated in the US, e-cigarette sales have seen a rapid rise unparalleled by any other non-combustible nicotine delivery system. The main components of the e-cigarette include a battery, a cartridge with nicotine dissolved in propylene glycol or vegetable glycerol, and a heater that aerosolizes the nicotine—propylene glycol solution. When the user puffs on the end of the device and creates a vacuum, the battery powers the heater and creates aerosol, which is drawn into the mouth piece and inhaled (Figure 3). E-cigarettes come in many styles and are rapidly evolving. This was true for first gen e-cigs. Later models have a button to push on the battery, which creates a bolus of vapor ready for immediate inhalation when the e-cig reaches the mouth.

Figure 3. Schematic for key components of the e-cigarette (image taken from the internet).

## THEORETICAL CASE FOR E-CIGARETTE HARM REDUCTION IN SMOKERS WITH CANCER

### TOXICOLOGY

E-cigarettes are not currently regulated, and the Food and Drug Administration has required no information from manufacturers on their ability to deliver nicotine and potential toxicity.

However, compared to cigarettes, they should deliver comparatively fewer toxic chemicals to the lung; available evidence strongly suggests this is true. Compared to tobacco smoke, studies have found e-cigarette smoke to be substantially lower in toxic content, cytotoxicity, and adverse side effects. One laboratory study comparing the toxicity profile of e-cigarette aerosols and tobacco smoke found that known tobacco toxins in e-cigarette aerosols were 100 to 1000 times lower than those found in tobacco smoke. Another FDA study found that carcinogenic tobacco specific nitrosamines in e-cigarette vapor was 8.2 ng/g, similar to the level in nicotine patch users (8.0 ng/g) and much less than the level in Marlboro cigarette smoke (6260ng/g). Another study found that toxic metabolites of cigarette smoke were greatly reduced in the urine of e-cigarette users compared to smokers.

Studies have also reported that e-cigarette use had no inflammatory effect on complete blood count indices, nor did it cause significant reduction in lung function (3% reduction FEV1/FVC) compared to cigarette smoke (7% reduction FEV1/FVC), and that e-cigarette use had no negative effects on myocardial function. Based on these and other studies, Public Health England has published a public statement that e-cigarettes are 95% safer than smoking.

[figure not shown]
Although e-cigarettes appear to have much lower toxic potential compared to cigarettes,

and are being embraced by some public health programs, they are not free from toxicity. Because of the lack of regulation of these products, we are now faced with an array of products, and no standardization of nicotine concentration, flavoring, and contaminant allowance. Lipoid pneumonia has been reported in one e-cigarette user, probably as a result of flavoring oils or oil contaminated glycerol. Use of high voltage batteries in refillable tank devices converts propylene glycol at very high temperatures to formaldehyde, but not to the levels found in tobacco smoke. Data are starting to appear that suggest that some of the flavor components of e-cigarettes may affect lung epithelial cells and inflammation, and even nonflavored vapor affected macrophage-moderated inflammation in mice exposed to the vapor. Thus, the sum of the limited data available so far suggests that, compared to cigarette smoke, e-cigarette vapor exposes users to much lower levels of toxins. While it remains unknown what the impact on health or oncological outcomes of e-cigarettes may be, the factors outlined above suggest a clear theoretical safety advantage over continued use of combustible tobacco products for patients with cancer. Given almost universal access to these products and the fact that cancer patients are using them, we have an obligation to determine how they affect consumption of combustible tobacco and whether their use affects intermediate medical outcomes. That is the overarching purpose of the present research.

## NICOTINE DELIVERY

Much of the nicotine from cigarettes is delivered to the brain by arterial circulation within seconds of puffing on the cigarette. This is one of the reasons for high abuse liability for cigarettes. Nicotine delivered from the oropharynx (e.g., when smokeless or nicotine gum is used) enters the venous blood and passes through the liver before going to the brain. This not only delays its delivery to the brain, but it lowers the dose because some of the nicotine is changed to cotinine in the liver. For e-cigarette aerosols, about half the nicotine absorbed is delivered through the alveoli, with the other half being delivered to the venous circulation through absorption from the oropharynx and bronchial tree. Delivery of nicotine is improving as e-cigarette manufacturers improve design. First generation e-cigarette devices, released between 2008 and 2010, delivered nicotine primarily to the mouth and oropharynx and could not product plasma nicotine concentrations equivalent to cigarettes (blue line in Figure 4 below).

[figure not shown]
Nicotine absorption from new generation devices (produced after 2010, red line in Figure 4) are able to equivalent levels of plasma nicotine, but only after 20-30 minutes of puffing. However, nicotine delivery from e-cigarettes has been shown to improve with practice, and more recent studies find that experienced users of some products can quickly deliver cigarette-like nicotine doses.

## BEHAVIORAL ADVANTAGES

Despite some disadvantages of nicotine delivery compared to cigarettes, e-cigarettes represent an improvement in nicotine delivery compared to available nicotine replacement products, such as nicotine gum or patch, products that were intentionally meant to be slowly absorbed. Part of the appeal of the e-cigarette is in how it mimics the behavioral process of smoking. The importance of the behavior in maintaining the smoking habit was recognized over 30 years ago by chief Philip Morris scientist William Dunn, who stated, “The smoking act has many dimensions. The motor aspects, drawing the smoke into the mouth, inhaling the smoke into the lungs ... taste and olfactory sensations are elicited, sensations are elicited when the smoke is drawn down into the lungs, psychosocial symbolism is imparted to the person, and a large number of chemical compounds pass rapidly into the bloodstream.” Nicotine replacement therapy emphasizes the effects of one of those compounds and largely ignores the important behavioral aspects of the habit. The effect of the behavioral components of the e-cigarette are apparent in a study of e-cigarette use and cigarette craving. As illustrated in Figure 5 below, e-cigarette use was associated with substantial reductions in cigarette craving, and these immediate reductions were independent of whether the device contained nicotine.

Figure 5. Craving to smoke a cigarette as a function of time and whether the smoker was inhaling a cigarette or an electronic nicotine delivery device (ENDD) with and without nicotine or a nicotine inhaler (one form of nicotine replacement therapy). Taken from Bullen, et al. 3

### E-CIGARETTE REGULATION: IMPLICATIONS ON STUDY DESIGN

As detailed below, the specific aims of this project are to determine the appeal and toxicity of e-cigarettes in current smokers with a smoking-related cancer. This is NOT a smoking cessation study; instead, it examines changes in intake for two tobacco products when administered together. There is a regulatory basis for the decision to focus on appeal and toxicity, and not smoking cessation. When e-cigarette devices first attempted to enter the US market, the Food and Drug Administration (FDA) blocked shipments on the basis that e-cigarettes were unapproved drug delivery devices and must first pass through FDA's New Drug Application process before they could be legally sold. E-cigarette manufacturers sued, arguing that e-cigarettes contained nicotine derived from tobacco and were therefore a tobacco product; the US Court of Appeals (Washington DC) ruled in their favor; and the FDA decided not to seek further review. The FDA then determined that they would "deem" e-cigarettes to be covered under the *Family Smoking Prevention and Tobacco Control Act* (deeming is in process at this date). In the meantime, the FDA has determined that any evaluation of the e-cigarette product for a therapeutic endpoint (such as treating nicotine addiction) requires an Investigational New Drug Application (involving animal pharmacology and toxicity studies, manufacturing information on the product, etc.). This regulation does not allow scientists not closely affiliated with an

e-cigarette company to study these products as therapeutic devices. Moreover, e-cigarette companies have made it clear in US courts that they do not seek approval as a drug delivery device.

The Center for Tobacco Products (CTP) at FDA is charged with regulating the tobacco market under the *Family Smoking Prevention and Tobacco Control Act*, which charges the FDA, among other things, “to promote cessation to reduce disease risk and the social costs associated with tobacco-related diseases.” CTP funds investigators to help the agency compare tobacco products with respect to three issues of interest—their relative appeal, toxicity, and effect on health. This leaves scientists the option of studying the e-cigarette as a modified risk tobacco product in smokers with respect to those three types of outcomes. The ultimate goal is to reduce the harm caused by cigarettes and other combustible tobacco products by substituting less toxic delivery devices for the primary drug, nicotine. This pilot project begins this line of investigation with a short-term study of e-cigarette appeal and toxicity among cancer patients that smoke.

## **TRIAL PROTOCOL**

### **STUDY DESIGN**

We will enroll 40 chronic smokers from the Norris Cotton Cancer Center and the White River Junction VAMC, approximately 15 of which will be accrued from the White River Junction VAMC. Participants will be given access to e-cigarettes for a 9-week period. Consecutive patients with stage I-IV aerodigestive tract cancers or bladder cancer who are current daily smokers will be identified two ways:

- 1) Clinic Recruitment - Potential participants will be identified by the treating physician during routine clinic visits. Patients will be advised to quit smoking as per the standard of care. Any patient wishing to quit smoking will be referred for smoking cessation counselling through the DHMC program, the White River Junction VAMC program, or their state help-line. Once eligibility is confirmed and informed consent is obtained and signed, patients will be enrolled in the study.
- 2) EMR Recruitment: In a recruitment strategy that parallels clinic recruitment, we will use the EMR to identify all potentially eligible smokers (with the diagnosis of aerodigestive tract cancers or bladder cancer) that have been seen in the NCCC in the past 3 years. EMR records will be searched by the D-HRDS Analytics Institute who will then forward a list of potential subjects to the project coordinator with their diagnoses and contact information, consistent with our partial HIPAA waiver. The project coordinator will then send this list of potential subjects to their providers to be approved to be contacted about the study. Approved potential subjects will then be contacted by mail through a letter from their NCCC oncology group. The subjects will have an opportunity to opt out of receiving a phone call through a prepaid return mailer or by calling a telephone number. If we do not hear from them in 2 weeks, we will then attempt to call them. We will attempt to call one time a week for 3 weeks. If there is no answer we will leave a brief, generic message. The call will assess their smoking status, and their willingness to quit. Nonsmokers are not eligible. If they smoke and are interested in quitting, they will be referred to their state quit line. If they are not interested in quitting at this time, they will be

offered participation in the study, and we will confirm eligibility. The mailing will include: A letter from their oncology group at NCCC, the brochure for their state quit line, a handout about the study, and a paper to return to us in a postage-paid envelope. If they return the paper to us requesting a referral to the quit line we will notify the D-H smoking cessation specialist. He/She will then process the referral to the quit line in EDH. The patient will then be contacted directly by the quit line. We will also provide them with their state smoking cessation help-line numbers. If they return the paper to us indicating they do not wish to quit and would like more information regarding the study, a coordinator will contact them.

Once enrolled, participants will receive the e-cigarette product described below, will be instructed on use of the e-cigarette, and given a supply that is approximately equivalent to their current nicotine intake. They will be told that e-cigarettes are theoretically safer than cigarettes, and that this trial aims to test how appealing the product is for smokers not willing to quit consuming nicotine.

We have opted to use e-cigarette products produced by Halo, a US manufacturing company that emphasizes the purity of its products and its approach to quality control in the manufacturing process. Patients will be given Halo Triton, which uses a leak-proof refillable tank system that has had a recent technological update. The patient will be shown how to fill the tank and will be observed filling it. Those not able to manage the tank refill will be given Halo G6 leak proof prefilled cartomizers (the part of the e-cigarette that contains the nicotine solution and the heating filament); these can be substituted for the tank on the Triton battery. The starter kit that will be distributed to patients is illustrated in Figure 6.

HALO manufactures its e-cigarette and the nicotine solutions in the United States. The HALO solution e-cigarettes contain 0, 12, 18, 24, or 36 mg/ml nicotine. We have been advised to begin our participants with 18mg/ml and move up or down based on patient preference. E-cigarette liquid also comes in many flavors, and we have decided to allow participants to choose from four options. Halo has agreed to provide us with the names of their 4 highest selling liquids. They have shared an ingredients list with the Drs. [name] and [name] for the purposes of adverse event monitoring and in the event that our IRB members request information about the ingredients.

Figure 6. Starter kit for the Halo Triton tank.

Coordinators will assess participants at baseline and weeks 3, 6, 9, and 12. Although most of our patients are expected to have completed their therapy, the schedule is designed to integrate with return schedules for many chemotherapeutic regimens, if possible. We have considered the concern that chemotherapy could affect cigarette consumption or excretion of nicotine metabolites. According to our clinicians, the current chemotherapy regimens for these cancers are not associated with severe symptoms, such that patients rarely decrease their smoking during treatment. Nevertheless, we will assess the severity of 6 common chemotherapy side effects at each visit so that may be entered as a covariate in our analytic models. Regarding metabolites, for nicotine, the major metabolite cotinine is formed via CYP2A6 and CYP2B6 metabolism, and the traditional cytotoxic chemotherapeutic agents used in the cancer treatment are not known to affect the activity of these CYP450 /UGT enzymes significantly. Additionally, cyclical cytotoxic chemotherapy is not given every day throughout a cycle. The most well characterized carcinogens of smoking so far are NNK (4-(methylnitrosamino)1(3-pyridyl)-1-butanone) and NNAL (4-(methylnitrosamino)1(3-pyridyl)-1-butanol). These carcinogens are also metabolized by some of the same enzymes that metabolize nicotine including CYP2A6, UGT2B10, UGT1A4 and CYP2A13, so these should not be affected by most chemotherapeutic regimens.

Coordinators will assess eligibility, collect specimens, administer CO2 measurements and administer the surveys during the baseline and follow up visits.

## PARTICIPANTS

### Inclusion Criteria:

- 1) Histological or cytological diagnosis of aerodigestive tract cancers or bladder cancer within the past 5 years (more than one tobacco-related malignancy is allowed)
- 2) AJCC stages I-IV
- 3) Daily smoking (at least 10 cigarettes per day for 10 years) and breath CO2 ≥8 ppm
- 4) Does not wish to quit smoking now (anyone wishing to quit smoking will be referred for smoking cessation counselling through the WRJ VAMC or DHMC program)
- 5) May be receiving anti-cancer agents
- 6) Age 18 or older
- 7) Fluent in English
- 8) Patient must be capable and willing to provide informed written consent for study participation
- 9) Able to participate in study visits

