## ABSTRACT

Smoking causes many cancers but also affects survival and quality of life. Currently, the only option available to smokers who present with cancer is to quit, a notoriously difficult undertaking. E-cigarettes represent a modified-risk tobacco product that could reduce toxicity and improve medical outcomes. We test the appeal of e-cigarettes in cancer patients that smoke, and the impact of their use on excretion of smoke-related toxic metabolites. This pilot study tests the feasibility of a larger randomized trial to examine the effect of e-cigarette use, on measures of smoke-related toxicity and medical outcomes.

We will test feasibility in 40 smokers with aerodigestive tract cancers or bladder cancer, recruited over the course of nine months. In this 12 week single-arm study, smokers will be recruited from oncology and surgical clinics that treat these cancers, supplied with a current generation e- cigarette product and will return to clinic every 3 weeks for assessments on their e-cigarette and cigarette use along with markers for toxicity from tobacco smoke inhalation.

The overarching aim of the study is to determine the appeal of e-cigarettes as measured by the degree to which smokers with cancer adopt their use over the 9 weeks they are supplied with product. We will measure past use of e-cigarettes and cigarettes at baseline, 3, 6, 9, and 12 weeks. We will also assess the effect of e-cigarette substitution on toxicity by measuring expired carbon monoxide and urine NNAL, a carcinogenic metabolite of cigarette smoke. This translational research involves a multi-disciplinary team of prevention scientists, tobacco-use experts, statisticians, cancer clinicians, and psychiatrists and uses NCCC and White River Junction VAMC statistical and clinical trials resources.

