## RECRUITMENT

Potentially eligible patients will be identified by clinician-researcher collaborators and through clinical trials nurses or clinical research coordinators, who monitor the cancer patient population for recruitment into clinical studies. Patients may be identified in multiple clinical settings, including outpatient clinics and the infusion suite. Once a potentially eligible patient is identified, a referral will be made to the site coordinator, who will meet with the patient, confirm eligibility, and obtain consent for the patient to participate in the study, and register the patient in the Velos e-Research database. (If a site coordinator is unable to utilize Velos, that coordinator will submit participant data to another coordinator with access and it will be entered into the Velos e-Research database.) The coordinator will conduct baseline web assessments, provide e-cigarettes and instruction on how to use the product, and conduct all follow up assessments.

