## STUDY TIMELINE AND FOLLOW-UP

The trial is designed to allow for patient visits every 3 weeks for 12 weeks. The coordinators will work with the participant and the participants' medical care teams to schedule and conduct the visits. We will contact enrolled subjects for follow-up at 6 and 12 months after enrollment. Each time, we will attempt to contact the subjects 3 times by phone over a period of 3 weeks. During the call the subject will be asked if they are still using an e-cigarette, what brand they are using, what concentration of nicotine they use, how many times a day they use it, and how often they currently smoking any combustible tobacco products.

Participants will receive free e-cigarette products for the first 9 weeks of the trial and \$20 for each visit (\$100 total). Participants that travel more than 20 miles one-way for a study-only visit (no other appointments scheduled on the day of their study visit) will be given a \$10 gas card.

Time	Baseline	3 weeks	6 weeks	9 weeks	12 weeks
Activity	Consent; survey; ecig instruction; urine; CO	Survey; ecig refill; urine; CO	Survey; ecig refill; CO	Survey; qualitative interview; urine; CO	Survey; CO
Compensation	\$20	\$20	\$20	\$20	\$20

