**Toxicity Assessment:** Our measures of toxicity, urine NNAL, 1-HOP and CO2 will be compared between the baseline and 9-week assessments via paired t-test. For NNAL, assuming a standard deviation of change in this measure of 3.8 pmol/mg creatinine (as was seen in Joseph et al. 2008), with 40 participants, this test will have 80% power at the two-sided 0.05 significance level to detect a change from baseline of 1.7 pmol/mg creatinine. There is not enough information available on 1-HOP to perform a test of power, so analysis of this metabolite is considered exploratory. For expired CO, assuming a standard deviation of change in this measure of 17.0 ppm, with 40 participants, a paired t-test comparing baseline to 9-week will have 80% power at the two-sided 0.05 significance level to detect a change from baseline that is 7.7 ppm. Additionally, since CO2 will be measured several times throughout the treatment period, the trajectory of change over time in this measure will be modeled via linear mixed effects models including random intercept and slope terms to account for repeated observations within individual. With repeated measurements of CO, the power for the mixed model will be greater than that of the paired t-test of change from baseline to detect this change over time.

We will also evaluate toxicity by analyzing cotinine level to assure that the adverse effect of increased cotinine (resultant from increased e-cigarette usage without similar decrease in combustible cigarettes). To do this, we will compute the number of participants with an increase in cotinine over the course of the study and consider this an adverse event. With 40 participants, confidence intervals around this adverse event percentage will be at most 0.32 percentage points. The table below gives the probability of observing at least 1 participant with an increase in cotinine given different true percentage of participants with this adverse event. For example, if the population-wide true percentage of participants with cotinine increase is 0.5%, then the probability of observing at least 1 of the 40 study participants with an increase is 0.18.

True percentage of participants with increase cotinine	Probability of observing at least 1 adverse event (increase in cotinine)
0.5%	0.18
1%	0.33
2%	0.55
5%	0.87
10%	0.99

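### As scheduled, the breath reading that qualifies a patient (at least 8 ppm) appears also to be the CO outcome baseline, which builds a modest regression to the mean into the CO comparison, in the direction of H2

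*Combined protocol and SAP*

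**What the plan says.** Inclusion criterion 3 in the combined protocol and SAP combines a smoking history with a lower limit on a breath measurement: "Daily smoking (at least 10 cigarettes per day for 10 years) and breath" reading of at least 8 ppm. (The documents label the measure both CO and CO2. The ppm unit and the breath meter point to CO; the labels should be reconciled, but nothing here turns on it.)

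Three places bear on when that reading is taken. Study Design states: "Coordinators will assess eligibility, collect specimens, administer CO 2 measurements and administer the surveys during the baseline and follow up visits". Recruitment sends the patient to a site coordinator, "who will meet with the patient, confirm eligibility, and obtain consent for the patient to participate in the study", who then runs the baseline assessments and provides the product. The visit table under Study Timeline and Follow-up has five visits, and its baseline cell reads "Consent; survey; ecig instruction; urine; CO". No screening visit, repeat reading or averaged baseline is described, and the telephone call used in EMR recruitment cannot supply a breath reading.

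The design has no comparison group ("In this 12 week single-arm study"). H2 predicts that CO and urine NNAL will be lower after 9 weeks. Under Toxicity Assessment, "a paired t-test comparing baseline to 9-week will have 80% power at the two-sided 0.05 significance level" for a change of 7.7 ppm, with 40 participants and an SD of change of 17.0 ppm. The CO trajectory is also to be fitted with a mixed model with random intercept and slope. Neither analysis allows for selection on the baseline value, and regression to the mean is not mentioned.

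**The concern.** A reading that varies from day to day is used with a lower limit to decide who enters. People whose reading is low on that day are turned away, and people whose reading is high by chance are kept. No limit applies at week 9. If the qualifying reading is also the outcome baseline, the group mean is expected to fall even when nobody changes their smoking.

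With no control arm, nothing absorbs that fall, and the paired test counts it toward H2. The mixed model starts from the same selected value, so it does not remove the effect. Exhaled CO is listed among the primary outcomes, and the pilot is meant to inform a larger trial. At stake are a false-positive rate above the nominal level for CO and a CO change estimate that is somewhat too large.

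**Working it through.** **Inputs from the documents.** Entry limit 8 ppm; n = 40; SD of change 17.0 ppm; two-sided 0.05; detectable change 7.7 ppm.

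**Assumed, because the documents do not give them.** Mean CO, between-person SD, between-visit correlation r, and the shape of the distribution. An SD of 17 with r = 0.5 agrees with the stated SD of change, since 17 × √(2 × (1 − 0.5)) = 17.

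**Step 1: reproduce the stated figure.** Noncentrality is 7.7/17.0 × √40 = 2.86. With 39 degrees of freedom the power is 79.8%, and the change detectable with 80% power is 7.72 ppm. The normal approximation gives 17 × (1.960 + 0.842)/√40 = 7.53. The plan's 7.7 ppm reproduces.

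**Step 2: expected fall with no true change.** For log-normal readings with the same mean and SD at both visits:

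- s² = ln(1 + (SD/mean)²), and m = ln(mean) − s²/2
- log-scale correlation q = ln(1 + r(SD/mean)²)/s²
- a = (ln 8 − m)/s, so the share failing the limit is Φ(a)
- expected fall = mean × [Φ(s − a) − Φ(qs − a)]/Φ(−a)

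Mean 20, SD 17, r 0.5: s = 0.737, m = 2.724, q = 0.567, a = −0.874. Fall = 20 × (0.9464 − 0.9018)/0.8089 = 1.1 ppm.

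Mean 25, SD 17, r 0.5: s = 0.617, m = 3.029, q = 0.547, a = −1.540. Fall = 25 × (0.9845 − 0.9698)/0.9382 = 0.4 ppm.

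Mean 15, SD 10, r 0.5: s = 0.606, m = 2.524, q = 0.546, a = −0.733. Fall = 15 × (0.9098 − 0.8564)/0.7683 = 1.0 ppm.

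**Step 3: chance of a significant fall.** Pairs were simulated with no true change and kept if the first reading was at least 8 ppm. Groups of 40 were then tested with the two-sided paired t-test. The nominal chance of a significant fall is 2.5%.

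| Log-normal, r = 0.5 | Share failing 8 ppm | Spurious fall (ppm) | Significant fall |
|---|---|---|---|
| mean 25, SD 10 | under 1% | under 0.1 | 2.5% |
| mean 30, SD 17 | about 1% | 0.1 | 2.6% |
| mean 25, SD 17 | 6% | 0.4 | about 3.5% |
| mean 20, SD 17 | 19% | 1.1 | 6.4% |
| mean 15, SD 10 | 23% | 1.0 | about 10% |

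The share of candidates who would fail the limit largely drives the result.

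**Step 4: effect of the shape assumption.** For normal readings the expected fall is (1 − r) × SD × φ(a)/Φ(−a), with a = (8 − mean)/SD. Mean 22, SD 17, r 0.5 gives a = −0.824 and 0.5 × 17 × 0.284/0.795 = 3.0 ppm, with 21% significant falls. That model puts Φ(−22/17) = 10% of readings below zero, which is impossible for CO, so it overstates the effect.

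**The case against.** The strongest reply is that no sentence makes one reading serve both purposes. The baseline cell does not exclude a qualifying breath followed by a baseline breath, and the number of breaths per visit is left to the device instructions. That stands: a reader might infer that the plan prescribes a shared reading, but this is a strong inference from the schedule, which shows no other reading.

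Second, candidates must already smoke at least 10 cigarettes a day for 10 years, so 8 ppm may exclude few of them and the bias may be close to nil. That also stands, and it is why the size has to be given as a range. It does not remove the point: the limit matters only if it excludes someone, and then it biases.

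Third, a reader might take the larger error rates at face value. Those of 20% and above come mostly from normal models that allow negative CO. Log-normal readings reach roughly 3 ppm and one chance in six only at mean 15, SD 17, r 0.4, where about 41% of candidates would fail the limit. Neither is a fair summary.

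Fourth, a reader might conclude that H2 as a whole is compromised, or that the artefact could account for the planned effect. H2 also names NNAL, which has no entry threshold and is affected only through its correlation with CO. No scenario examined produces a fall of 7.7 ppm. That figure is the change detectable with 80% power, however. A small bias can still raise the false-positive rate without reaching it.

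Finally, this is an uncontrolled pilot in which any CO fall already needs caution. That limits the weight of the point, but a known artefact that is cheap to reduce is still worth reducing.

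**Conclusion.** The point holds for CO and is modest in size. The schedule leaves a single pre-product reading at the visit where eligibility is confirmed, and a lower limit on that reading biases the baseline-to-week-9 change toward H2 in both the paired test and the mixed model.

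Assuming log-normal readings consistent with the stated SD of change (mean 20 to 25 ppm, SD 17, r 0.5), the artefact is about 0.4 to 1.1 ppm and the one-directional error about 3.5% to 6.4% instead of 2.5%. With almost everyone above 8 ppm it vanishes. With about a quarter failing (mean 15, SD 10) it is about 1 ppm and 10%. These figures rest on an assumed distribution, and the shared reading is itself inferred. They do not invalidate the CO outcome, but CO as planned is a somewhat less secure marker than NNAL.

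**What to change.** State which breath reading qualifies the patient, record it separately, and do not use it as the outcome baseline. Take a fresh CO reading before dispensing, at a later contact where one already occurs, and use that in the paired test and the mixed model. If the fresh reading correlates with the qualifying reading no more than the week-9 reading does, the expected no-effect change returns to zero and the chance of a significant fall to 2.5%. The 7.7 ppm is unchanged if the SD of change stays at 17.0.

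Where both readings must fall on one day, the repeat removes only part of the bias, because the two share that day's variation. For that case, prespecify a sensitivity estimate of the CO change that treats the qualifying value as truncated at 8 ppm on the log scale. Report it beside the primary test, not as a condition for claiming a CO reduction; with 40 people it is too imprecise and too dependent on the assumed distribution to decide the matter. It would also help to report how many candidates fail the 8 ppm limit, since that share indicates how large the bias can be.

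The cost is one extra breath on a meter already owned, a slightly smaller CO effect, and a distributional assumption in the sensitivity analysis. Insisting on a separate day could mean an extra visit for patients recruited through the EMR, so it is asked for only where a contact already exists. If enrolment is already complete, only the sensitivity estimate remains available.
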